1. OBSTRUCTIVE SLEEP APNEA (OSA)
2. APNEA-HYPOPNEA INDEX (AHI)
3. POLYSOMNOGRAPHY (PSG)
4. CONTINUOUS POSITIVE AIRWAY PRESSURE MACHINE (CPAP)
5. EPWORTH SLEEPINESS SCALE (ESS)
6. STOP QUESTIONNAIRE (SQ)
7. STOPBANG QUESTIONNAIRE (SBQ)
8. BERLIN QUESTIONNAIRE (BQ)

CHAPTER 1

INTRODUCTION

1.1 INTRODUCTION / BACKGROUND RESEARCH.

Obstructive sleep apnea (OSA) has been one of the topmost global health problems. It is an underdiagnosed disease which have a huge burden on healthcare if left untreated. Almost 80-90% of adults are underdiagnosed of OSA ⁽¹⁾.

Obesity primarily is one of the supreme risk factors for developing OSA. Globally, obesity cases have risen affecting almost two billion people. According to National Health and Morbidity Survey (NHMS) 2019, 1 in 2 adults in Malaysia were overweight or obese. Statistics showed, 54.7% are females, 63.9% are of Indian ethnicity and 60.9 % falls in the age group of 55-59 years old ⁽²⁾. Report from World Obesity Atlas 2023 predicts that adult obesity will rise 4.7% annually from 2020 – 2035, while child obesity will increase by 5.3% per year over similar timeline ⁽³⁾. Overweight individuals will have a significant economic impact on Malaysia's Gross Domestic Product (GDP) by 2035 by 2.8% which is estimated to be about RM 3.2 trillion ⁽³⁾.

Sequelae of OSA is divided into two (cardiovascular-metabolic effect and neurocognitive effect). This group of patients are at high risk of developing hypertension, insulin resistance, dyslipidemia which then leads to pulmonary hypertension and heart failure. More importantly, from the neurocognitive point of view, persistent sleep deprivation will lead to poor concentration, impaired memory, personality changes affecting overall self-performance which can lead to depression and compromising safety as they have higher risk of work-related accidents.

Therefore, in our study, we would like to educate our group of patients regarding risk factor and early diagnosis of OSA hence to offer the appropriate treatment. In this study, our patients will compare the difference in the usage of 2 types of continuous positive airway pressure machine (CPAP) as the mainstay treatment of OSA ⁽⁴⁾. They will then determine the most accessible and preferred machine to ensure compliancy thus preventing the unwanted consequences of the disease.

CHAPTER 2

LITERATURE REVIEW

OSA is defined as a sleeping disorder in which the upper airway collapse which results in partial (hypopnea) or complete (apnea) breathing cessation ⁽⁵⁾. An apneic episode may last at least 10 seconds during sleep. Most pauses last between 10 to 30 seconds but may persist a minute or longer ⁽⁵⁾. This will lead to sudden desaturation with oxygen falling as much as 40 percent or more in severe cases ⁽⁵⁾. In response to that, the body will try to compensate by partially being awakened to restore normal breathing. This cycle continues hundreds of times overnight resulting in poor quality of sleep and increases daytime sleepiness. People with OSA snores loudly and have period of silence when the airflow is reduced or blocked. They also make snoring or choking or gasping sounds when their airway reopens.

OSA occur in all age, but has its prevalence in between middle and older age group of male, and postmenopausal female. The risk prevalence of OSA in Asian population ranges between

4.98 % to 27.3% ⁽⁵⁾. Multiple risk factors are known. These includes obese patients with BMI > 30kg/m², patients with large neck size, Down syndrome patients, patients with abnormalities of the bony and soft tissue structure of the head and neck, children with large tonsils or adenoid, and patients with acromegaly and hypothyroidism ⁽⁵⁾.

Symptoms of OSA are fatigue, daytime sleepiness, snoring, and drooling. They also complain of headache and tendency to fall asleep while driving or watching television. They are more likely to be involved in motor-vehicle accident ⁽⁶⁾. The American Academy of Sleep Medicine reported that 46% of the people having at least mild sleep apnea, 34% have frequent snoring, 30% have insomnia symptoms and 25% reported to have excessive daytime sleepiness ⁽⁷⁾.

OSA leads to multiple major contributors of respiratory and heart diseases. Theoretically, OSA induces a chronic inflammatory state. It has been shown to stimulate white adipose tissue (WAT) leading to production of inflammatory mediators such as TNF- alpha, IL-6 and IL-8. Due to intermittent hypoxemia and recurrent hypercapnia, it stimulates the sympathetic activity, increases systemic inflammation and increases oxidative stress. It results in endothelial and metabolic dysfunction and increases the prevalence of hypertension and cardiovascular disease risk ⁽⁸⁾.

Shah et al assessed whether OSA increase risk of CV events. They found that despite controlling other CV risk such as diabetes, hypertension, alcohol and tobacco usage, OSA has increase the CV outcome risk ⁽⁹⁾.

The prospective sleep heart study (SHHS) was done to establish the association between OSA and incident coronary artery disease and heart failure. For the purpose of data collection and analysis regarding incident coronary disease, the first occurrence of myocardial infarction, coronary heart disease, death or revascularization were recorded. The rate of CHD was 20.1% per 1000 person – years of follow-up in men and 8.7% events per 1000 person-years of follow up in women. Event rates increased with severity of OSA in men ⁽¹⁰⁾.

OSA is a contributing factor for heart failure as well. Paulina et al. demonstrated of sleep breathing disorder was 81% in 316 patients, 30% of whom classified as Central sleep apnea and 70% as OSA ⁽¹⁰⁾. Sympathetic activation is the triggering factor for heart failure to occur. Also, the high negative intrathoracic pressure exerted during inspiration through a narrow or occluded upper airway may increase pulmonary capillary fluid efflux contributing to interstitial edema. Increased sympathetic activity leads to increase angiotensin II release promoting aldosterone production. Aldosterone increases water and salt resorption and leads to increase intravascular volume. In return, worsening hypertension and heart failure.

Atrial fibrillation is the most common arrhythmia linked with OSA. The prevalence is about 5% ⁽¹⁰⁾. OSA trigger its onset and contributes to its persistence. The known effect of hypoxemia and hypercapnia leads to tachycardia and hypertension. It increases the myocardial demand despite the restricted supply during these episodes. It leads to myocardial injury, conduction abnormalities, prolonged sinus node recovery time and later on fibrosis which will promote the development of AF.

As of today, we have 4 tools to stratify the risk of developing OSA. Stop questionnaire (SQ), STOP-BANG questionnaire (SBQ), Epworth Sleepiness Scale (ESS) and Berlin Questionnaire (BQ) are the current questionnaires available in literature ⁽¹¹⁾. STOP questionnaire consist of four yes/no answer questions assessing snoring, tiredness, observed apneas and high blood pressure. While the BANG portion assess the clinically observed quantities, with yes/ no answer. These includes BMI > 35kg/m², age > 50 years, neck circumference 40cm and male gender. Positive answer three out of eight indicates high risk for sleep apnea.

ESS assess the severity of daytime sleepiness in common daily situations based on eight administered questions with answer scoring from zero to three. A score of 11 or higher indicates excessive daytime sleepiness.

Berlin questionnaire is a set of questions consist of 11 questions focusing on three categories of apnea sign and symptoms: snoring, daytime sleepiness and obesity/ high blood pressure. 2 or more positive categories indicates high likelihood of OSA.

A meta-analysis found that the sensitivity and diagnostic odds ratio (DOR) of the SB were higher than BQ, SQ and ESS in detecting mild, moderate and severe OSA. However, the specificity of SBQ was lower compared to ESS. Hence the study concluded that SBQ was superior in detection of various severity of OSA in adults compared to others ⁽¹¹⁾.

The diagnosis is established only after an overnight sleep study called polysomnogram (PSG) is conducted. It is a consented procedure with a minimum of 6 hours study.

OSA can be divided into 3 types which are mild, moderate and severe based on the PSG report. Mild is defined as Apnea-hypopnea index (AHI) 5-15. Moderate is diagnosed when AHI is 15 – 30, and severe OSA is known when AHI > 30 ⁽¹¹⁾.

Treatment options includes non-surgical based or surgical based. Non-surgical based treatment advises for lifestyle modifications namely good dietary intake and weight reduction. Another lifestyle modification is targeting towards education of good sleeping hygiene such as avoiding daytime nap, fixed bedtime routine, avoiding alcohol, caffeine or heavy or spicy food prior bedtime and eliminating noises and lights ⁽¹²⁾. Positional therapy is also recommended for mild OSA. Patients are advised to stay off the back and raise the head of the bed to reduce symptoms ⁽¹²⁾.

Most common management of moderate to severe OSA is the use of Positive airway pressure (PAP) device ⁽¹²⁾. Its function is to hold the airway open by using air pressure that is introduced through the nasal mask or similar device ⁽¹²⁾. The needed amount of pressure set on the device is determined by PSG result or automated technique setting within the device itself ⁽¹²⁾. Most commonly used PAP device for moderate to severe OSA is the CPAP machine. This machine is proven to improve sleepiness, thus giving a better quality of life and most importantly is able to prevent the daunting consequences of persistent hypoxemia such as myocardial ischemia, stroke, arrhythmias and heart failure.

In European Respiratory Journal publish in 1998, survey of 3225 patients treated with CPAP for at least 6 months of treatment in which > 80% have reported symptoms improvement. ⁽¹³⁾

Meanwhile, according to British Cardiac Society by a study in October 2023, they reported impact of 12 weeks of CPAP usage and the clinical improvements in echocardiographic parameters of right ventricle. Improvement of Isovolumetric acceleration (IVA) by 0.5ms² and tricuspid annular plane systolic excursion (TAPSE) value significantly improve after twelve weeks of CPAP by 2.05mm. ⁽¹⁴⁾

Currently in Malaysia we have different companies offering different types of machines. The manufacturers are constantly improvising new technology in order to make the device more user friendly. Available options include conventional PAP machine with the newer smaller and portable machine such as AirMini.

According to research study by Brian W. Rotenberg, Claudio Vicini, Edward B Pang, and Kenny P Pang, adherence to CPAP has been a problem. In their review of 83 CPAP trials, the average patient in bed for 7 Hours across 83 closely supervised clinical trials was not using the machine in average of 32.9% of the night. This is a problematic percentage as multiple different RCTs have documented that a minimum level of 4H use of CPAP per night is required to gain benefit from it ⁽¹⁴⁾. Even though CPAP is the main gold standard treatment proposed,

however the real-world effectiveness of CPAP is low, with large number of patients abandoning the machine within one year of prescription (15)

Surgical therapy played an important role in surgically correctable obstructive lesion in upper airway among OSA patients. The type of surgical intervention is depending on the site and level of obstruction which may include nasal, palatal, oro-hypopharyngeal, maxillofacial, tracheostomy or hypoglossal nerve stimulation (12). Surgical options are currently vast and may change from time to time according to the latest surgical advances and technology.

CHAPTER 3

RESEARCH OBJECTIVES

3.1 Objectives

3.1.1 Primary

1. To compare the overall satisfaction using Visual Analogue Score 100mm among moderate to severe OSA patients between two types CPAP machine – conventional Airsense 10and AirMini CPAP.

3.1.2 Secondary

1. To evaluate the efficacy between two CPAP machine (conventional Airsense 10and AirMini CPAP) in terms of AHI reduction.
2. To compare the average 95th centile pressure required using conventional Airsense 10and AirMini CPAP
3. To determine the correlation between the satisfaction score and reduction of AHI using Airsense 10and AirMini CPAP machine.
4. To compare the difference between conventional Airsense 10and AirMini CPAP in terms of:
 - a) Air leak
 - b) Comfort
 - c) Compactness & portability
 - d) Maintenance & configuration

Hypothesis

- 1) Patient's overall satisfaction is better using AirMini CPAP compared to AirSense CPAP machine.
- 2) There is no difference in terms of AHI reduction and average 95th centile pressure required between AirMini CPAP compared to AirSense CPAP machine.

- 3) There will be positive correlation between overall satisfaction and AHI reduction for AirMini CPAP compared to AirSense CPAP machine.
- 4) There is improvement in air leak, comfort, compactness and maintenance in AirMini CPAP machine compared to AirSense CPAP.

3.1 Significance of Research

Consequences of OSA is detrimental in multiple level. It reduces work performance and quality of life individually. It causes healthcare burden later as it significantly increases the CV, stroke and other metabolic risk. Globally the government is bound to spend more to treat the affected group of people.

This research will give a comparison in overall satisfaction among the OSA patients using both conventional AirSense CPAP machine and AirMini CPAP machine and hence will enhance the compliancy among user and minimise unwanted complications following OSA.

CHAPTER 4

RESEARCH METHODOLOGY

4.1 Type of Study

This is a prospective cross over trial study of group of patients with moderate to severe OSA based on the severity of the AHI.

4.2 Study Design

4.2.1 Period of Study

September 2024 until December 2026.

4.2.2 Study Setting

This study will be conducted for all moderate to severe OSA patients in Hospital Canselor Tuanku Muhriz (medical and non-medical department).

4.2.3 Sampling Population

This study will be conducted either to inpatient setting or outpatient setting clinic. Selection of patients will include patients with BMI > 30, Neck circumference > 17cm. Age group of patients will include those who are 20-65 years old. Both female or male patients may be selected.

4.2.4. Type of Sampling

Type of sampling method in this study is convenient type of sampling.

4.2.5 Inclusion criteria

- Aged \geq 18 years.
- Patients diagnosed with moderate to severe OSA (based on AHI classification from sleep study performed).
- Patients who are able to understand and answer the questionnaire given.

4.2.6 Exclusion Criteria

- Patients who are unable to give consent to the study.
- Patients who have been diagnosed with OSA and already on CPAP machine.
- Patients who had underlying Obesity Hypoventilation Syndrome (OHS).
- Patients who had underlying co-morbidities that worsen apnea symptoms, such as congestive cardiac failure, active malignancy, narcolepsy, active alcohol or drug abuse, treatment-refractory dementia, psychotic illness and active use of drugs that disturb the sleep architecture (i.e hypnotics or stimulants of central nervous system).

4.2 Study Protocol and Data Acquisition

This is a cross over trial that includes patients with medium to high risk of OSA according to STOPBANG score. Once these group of patients are selected, consent will be taken from them to go through a scheduled sleep study. Diagnosis is established after AHI score is concluded from the polysomnographic study. Those who are diagnosed with moderate to high AHI score will be recruited in this study. All subjects will be given a CPAP trial using both AirSense and AirMini model for 7 days each device. Upon recruitment, the subject will be randomised using 1:1 block randomisation either to receive Airsense CPAP machine or Airmini CPAP machine.

Those subjects that use AirSense CPAP machine first for 7 days will be given a set

of Questionnaire at the end of 7th day of the trial. Subsequently, they will be switch to use AirMini CPAP machine for another 7 days and the same set Questionnaire will be given on the 7th day of the trial. The type of the interface used will be based on subject's preferences, i.e., full face mask / nasal mask / nasal pillow, during the initial 1 – 2 days of CPAP trial. The same interface as per subject's preferences will be used throughout the CPAP trials for both AirSense as well as Airmini CPAP machine.

The Questionnaire given comprises of a 100mm Visual Analogue Score (VAS) for: 1) Overall satisfaction, 2) Air Leak, 3) Comfort, 4) Compactness & Portability, 5) Maintenance & Configuration. The data collected will be analyzed using SPSS Version 27.

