4.4 Sample Size

This is a cross-sectional prospective study; hence the sample size calculation will be based on Machin et al. (2018) - *Machin, D., Campbell, M. J., Tan, S. B., & Tan, S. H. (2018). Sample Sizes for Clinical, Laboratory and Epidemiology Studies. doi:10.1002/9781118874905*

[figure not shown]
Table 16.2 Flat rule-of-thumb for the total sample size of a two equal-group comparative External-Pilot trial (partly based on Whitehead, Julious, Cooper and Campbell, 2015, Table 4).

Reference	N_{Pilot}
Birkett and Day (1994)	20
Julious (2005)	24
Kieser and Wassmer (1996)	20 to 40
Sim and Lewis (2011)	≥ 55
Browne (1995)	60*
Teare, Dimairo, Shephard, et al (2014)	≥ 70

*Actually recommended 30 for a single-arm study

The sample size decided for this study was 40 subjects. Considering and taking into account of about 10% dropout / missing data, hence the total sample size that will be recruited for this study are 50 subjects.

Data Collection Pathway

CHAPTER 5

RESEARCH ETHICS

Approval from the Research and Ethics Committee of Universiti Kebangsaan Malaysia Medical Centre (UKMMC) was done. All the collected information will be strictly confidential and only accessible by the research team members. All patients will be kept anonymous and coded into the data collection sheet.

Participants will only be recruited in this study once informed consent given, and will be allowed to withdraw from the study at any point. The research will be conducted according to the standard of good clinical practice and the rights and safety of the participants are guaranteed throughout the study.

GANTT CHART

Progression/Timeline	January 2023-March 2023	March 2023-July 2023	July 2023-August 2023	September 2023-September 2025	September 2025-November 2026
Literature review and proposal write up					
Proposal submission and correction					
Presentation to ethics committee and approval					
Patient recruitment and conduction of study					
Statistical analysis and preparation of result					
Manuscript writing and submission					

REFERENCES

References

- 1) American academy of sleep clinical practice guideline (<https://aasm.org/resources/factsheets/sleepapnea.pdf>)
- 2) National health and morbidity survey (https://iptk.moh.gov.my/images_Booklet_NHMS_2019)
- 3) (<http://codeblue.galencentre.org/2023>)
- 4) Malayisa e-cpg management of OSA (<https://www.moh.gov.my>)

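### Satisfaction is rated only on day 7 of each device, so a subject who stops a device earlier may leave no score and fall out of the within-patient primary comparison

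*Protocol*

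**What the plan says.** Section 3.1.1 sets the primary objective: "To compare the overall satisfaction using Visual Analogue Score 100mm among moderate to severe OSA patients between two types CPAP machine". Section 4.2 Study Protocol and Data Acquisition makes the trial a crossover: "All subjects will be given a CPAP trial using both AirSense and AirMini model for 7 days each device". The order is randomised 1:1 in blocks.

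The same section fixes when the VAS is taken. For subjects who have the AirSense first for 7 days, the set is given "of Questionnaire at the end of 7th day of the trial". After the switch, "the same set Questionnaire will be given on the 7th day of the trial". Only this order is written out; I take the other to mirror it. No other rating time appears in the text at hand.

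Three further statements bear on early stopping:

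- Section 4.4 sizes the study "Considering and taking into account of about 10% dropout / missing data", and meets that loss by recruiting 50 subjects for a target of 40.
- Chapter 5 says that participants "will be allowed to withdraw from the study at any point". It mentions no questionnaire at that moment.
- Chapter 2 describes poor adherence as a known problem with CPAP, "with large number of patients abandoning the machine within one year of prescription".

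**The concern.** Stopping a device early and being dissatisfied with it are plausibly linked. A subject who gives up on day 3 has probably formed a clear opinion of the device, and the schedule has no point at which to record it. In a crossover, a missing score on one device removes the subject from the within-patient difference, so the complete pairs may over-represent people who tolerated both devices.

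Recruiting extra subjects restores the number of pairs but not the missing opinions. This is also not something to leave to the analysis plan. A model or an imputation rule can limit the damage, but it cannot recover a rating that was never requested. The timing of the rating is a data-collection rule, and the protocol is where it is set.

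**Working it through.** **1. The plan's own loss figure.** Section 4.4 gives a target of 40, about 10% loss and 50 recruited. Inflating 40 for 10% gives 40 / 0.90 = 44.4, so 45; 40 × 1.10 gives 44. Neither is 50. Going from 50 to 40 is a loss of 1 − 40/50 = 20%. That mismatch is a separate matter. Here I use the stated 10%: 0.10 × 50 = 5 subjects without a full pair, leaving 45.

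**2. Size of the shift.** Let Dc be the mean paired difference (AirMini minus AirSense) among completers, and Ds the mean difference that k early stoppers would have given. With 50 subjects,

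shift = Dc − [(50 − k) × Dc + k × Ds] / 50 = k × (Dc − Ds) / 50.

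The protocol gives no value for Ds or Dc, so these are assumptions:

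| k | Gap on the stopped device | Dc | Shift in size |
|---|---|---|---|
| 5 | 40 mm | 0 | 5 × 40 / 50 = 4.0 mm |
| 3 | 30 mm | 0 | 3 × 30 / 50 = 1.8 mm |

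The simple form needs Dc near zero. With Dc = 5 mm and five stoppers, the shift is 5 × (5 + 40) / 50 = +4.5 mm if they stop the AirMini (Ds = −40). It is 5 × (5 − 40) / 50 = −3.5 mm if they stop the AirSense (Ds = +40).

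**3. Against the precision.** The protocol states no SD. Assume an SD of paired differences of 20 to 30 mm.

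- 40 pairs: 20 / √40 = 3.16 mm; 30 / √40 = 4.74 mm.
- 45 pairs: 20 / √45 = 2.98 mm; 30 / √45 = 4.47 mm.

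With the 40-pair figures, the 4.0 mm shift is 4.0 / 4.74 = 0.8 to 4.0 / 3.16 = 1.3 standard errors. The 1.8 mm shift is 1.8 / 4.74 = 0.4 to 1.8 / 3.16 = 0.6.

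**4. Direction.** A simulation of 2,000,000 bivariate normal VAS pairs removed the lowest scorers on a device. It assumed a VAS SD of 15 to 25 mm, a within-subject correlation of 0.3 to 0.7 and a true AirMini advantage of 5 mm. The scores were not bounded at 0 and 100.

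| Who gives no score | Completers' difference (true value 5 mm) |
|---|---|
| 10% least satisfied with AirMini | 5.9 to 8.4 mm |
| 10% least satisfied with AirSense | 1.6 to 4.1 mm |
| 5% on each device | about 5.0 mm |

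In the last row the AirMini mean among completers is still 2.0 to 3.6 mm too high. The difference survives because both means are inflated alike. Bias in the comparison therefore needs unequal loss, and it can run either way.

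**The case against.** The best reply is that the protocol fixes a calendar time and nothing more. It does not forbid asking a subject who stopped on day 3 to fill in the form on day 7. Stopping a device is not the same as leaving the study, and the mention of 7 days of AirSense use can be read as describing the sequence, not a condition for receiving the questionnaire. This stands in part: a reader might infer that every early stopper leaves no score, and the text does not say so. It simply makes no provision, which leaves the matter to local habit.

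Second, the contents list names a data collection pathway and a data collection sheet. The pathway figure and the sheet are not in the text at hand, and either might hold an entry for early stopping. That limits the point to the visible text.

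Third, the evidence on frequency is thin. The abandonment statement in Chapter 2 concerns one year, not 7 days, so it gives no rate for this trial. The 10% in section 4.4 covers loss and missing data from any cause. Nothing gives a device-related stopping rate. The same mask type is used with both devices, so mask intolerance would tend to affect both and largely cancel in the difference.

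Fourth, handling of missing scores usually belongs in the analysis plan, and the protocol names no primary test; a paired comparison follows from the crossover but is not stated. A mixed model or a worst-score rule could keep such subjects in. That is fair for the analysis, but both would stand in for an observation that could have been taken directly.

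**Conclusion.** The point holds as a gap in data collection with conditional consequences. Followed as written, the schedule can lose outcome-related scores from the primary comparison, and the extra recruitment does not repair that.

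The size is modest. A shift of 1.8 to 4 mm, or about 0.4 to 1.3 standard errors, rests on assumed numbers of stoppers, assumed gaps, an assumed SD and a completers' mean difference near zero. The upper end puts all five losses on one device, all for dissatisfaction.

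Two stronger readings are tempting and not supported. One is that the bias runs towards zero or reverses the result. The direction depends on which device is stopped more often; loss on the AirMini exaggerates an AirMini advantage, and no scenario in the simulation ranges above reversed the sign. The other is that the comparison is biased in any event. With equal loss on both devices it is nearly unbiased, and only the separate device means are too high.

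This does not undermine the design. It is a cheap improvement that protects the primary outcome.

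**What to change.** Amend section 4.2 Study Protocol and Data Acquisition so that, for each device and in both orders, the same questionnaire is completed on day 7 or on the day the subject stops using that device, whichever comes first. Record the date of and reason for stopping. Still collect the other device's VAS from subjects who are willing.

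State that the stop-day score counts as that period's VAS in the primary comparison, and add a sensitivity analysis restricted to scores taken on day 7. If the data collection sheet already has such an entry, the section need only refer to it.

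The cost is a sentence or two in the protocol and, if not already there, a line on the sheet. The change concerns when a form is filled in and does not alter treatment. The downside is that a few scores will rest on fewer than 7 nights, and very early ones may partly reflect the interface choice made in the first 1 to 2 days. The recorded date and the sensitivity analysis let a reader judge that. Subjects who withdraw and decline the form remain missing.
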